#### 5.7. Use of Abbreviations

Any abbreviations used in data listings will be included in a key in a footnote, as appropriate.

[figure not shown]
#### 6. ANALYSIS POPULATIONS

The Intent-to-Treat (ITT) Population will comprise all enrolled participants who received the treatment injection, analyzed according to randomized Stage A treatment. The ITT Population will be the primary analysis population for efficacy.

The Safety Population will comprise all participants who receive any amount of study drug, analyzed according to treatment actually received.

Participants who are assigned a randomization number but withdraw prior to dosing will not be included in the safety analysis set.

CONFIDENTIAL Page 14 of 27

Final 2.0, 11 Oct 2021

Protocol No.: XT-150-2-0204 Sponsor: Xalud Therapeutics, Inc.

#### 7. SUBJECT DISPOSITION/BACKGROUND DATA

#### 7.1. Subject Disposition

Subject disposition and administration procedures recorded in the CRF are as follows:

- Written informed consent
- Randomization
- Administration of IP
- Study completion /discontinuation
- Protocol deviations
- Additional comments

Details of participation and inclusion in analysis populations will be listed by subject. Completion status will be summarized by dose level / treatment.

Details of administration of IP will be listed by subject. Exposure to IP will be summarized by dose level / treatment.

Protocol deviations will be listed by subject. A summary of protocol deviations will be prepared for inclusion in the clinical study report.

### 7.2. Baseline and Eligibility Assessments

Baseline and eligibility assessments are as follows:

- Demographic details
- History of osteoarthritis of the knee
- Other medical and surgical history
- Physical examination
- Focused analgesia selection test
- Serology (HIV/Hepatitis B and C)
- Pregnancy Tests

#### 7.3. Baseline Data Analysis

Demographics will be listed individually by subject and summarized by dose level / treatment and overall.

Medical history and physical examination data at baseline and results of tests performed for eligibility will be listed by subject.

Baseline assessments of on-study measures will be listed and summarized along with post-dose assessments, as described below.

CONFIDENTIAL Page 15 of 27

Final 2.0, 11 Oct 2021

Protocol No.: XT-150-2-0204 Sponsor: Xalud Therapeutics, Inc.

#### 8. SAFETY DATA

#### 8.1. Safety Assessments

Safety assessments are as follows:

- Adverse events and concomitant medications used:
  - Continuous monitoring throughout the study period
- Vital signs
  - (heart rate, systolic and diastolic blood pressure, respiratory rate, temperature and site collected)
- Clinical laboratory tests
  - Hematology: hemoglobin, hematocrit, total and differential leukocyte count, red blood cell count, platelet count
  - Serum chemistry: bilirubin (total and direct), alkaline phosphatase, aspartate aminotransferase (AST), alanine aminotransferase (ALT)
  - Coagulation: prothrombin time [PT] / international normalized ratio [INR] and either partial thromboplastin time [PTT] or activated partial thromboplastin time [aPTT]
- Physical examination including all major organ systems

#### 8.2. Safety Data Presentation and Analysis

All clinical safety and tolerability data will be listed for each subject.

Safety data will be summarized using descriptive statistics. Where summaries include changes from baseline, the relevant baseline value will be determined as described in Section 5.5 above.

All adverse events will be listed using MedDRA terms, as coded per the Data Management Plan. The number and percentage of subjects with at least one treatment emergent AE and the number of treatment emergent AEs reported will be summarized by dose level or treatment, grouped according to system organ class and preferred term, using descriptive statistics. The order for system organ class will be according to the Internationally Agreed Order, as per the guidance document MedDRA® *Data Retrieval and Presentation: Points to Consider*, specific to the MedDRA version used for this study. Summaries of TEAEs will also be presented by severity (graded according to the NCI CTCAE version 5.0) and by relationship to investigational product. In these summaries, subjects will be counted at most once per MedDRA term, for the AE of highest severity or least favorable relationship. Summaries will also be presented for SAEs and for AEs leading to study withdrawal.

Clinical laboratory parameters for hematology, serum chemistry, and coagulation will be listed. Summaries of reported results, including changes from baseline and medical

CONFIDENTIAL Page 16 of 27

Protocol No.: XT-150-2-0204 Sponsor: Xalud Therapeutics, Inc.

assessments, will be presented by treatment group and study timepoint. Individual subject profiles will be presented for any laboratory parameters with at least one post-dose value outside the laboratory's reference ranges and deemed clinically significant.

Vital signs will be listed and summarized by dose level / treatment and study timepoint. A summary of changes from pre-dose baseline will also be presented.

Changes in physical examination findings over time will be listed by body system for each subject. It is noted that any untoward findings identified on physical examinations after the administration of the first dose of study medication will be captured as an adverse event if those findings meet the definition of an adverse event as defined in the protocol.

Injection site examinations will be listed and summarized by dose level / treatment and study timepoint.

Any detection of anti-IL-10 antibodies will be summarized by treatment and timepoint.

#### 9. EFFICACY DATA

#### 9.1. Efficacy Assessments

Efficacy assessments will be recorded throughout the study, during Stage A and Stage B at each of the following study visits:

Stage A: nominally Days 7, 30, 60, 90, 120, 150, and 180.

Stage B: nominally Days 210, 240, 270, 300, 330 and 360

The primary efficacy outcome measure is whether the subject achieves at least a 30% improvement from baseline in WOMAC Pain Score (obtained from the KOOS questionnaire) at Day 180, as recorded on a 0 to 20 point scale with 20 being the maximum (worst) score.

Secondary efficacy outcome measures are:

- Change from baseline in the WOMAC Function Score (from KOOS questionnaire) at Day 180
- Change from baseline in the WOMAC Pain Score (from KOOS questionnaire) at Day 180 (this endpoint was inadvertently omitted from the protocol)
- Change from baseline in patient response at Day 180, using a scale of 1 5, to the
  OA question: "Considering all the ways the OA in your knee affects you, how are
  you doing today?", with 1 being very good (asymptomatic and no limitation of
  normal activities) to 5, very poor (very severe, intolerable symptoms and inability
  to carry out normal activities)

Additional endpoints include:

Final 2.0, 11 Oct 2021

Protocol No.: XT-150-2-0204 Sponsor: Xalud Therapeutics, Inc.

- Total and individual parameter scores for the Brief Pain Inventory of Intensity and Interference (BPI) (reported values and change from baseline)
- The Knee Outcome and Osteoarthritis Scores (KOOS) (reported values and change from baseline)

#### 9.2. Efficacy Data Presentation

Efficacy assessments will be listed for each subject.

The WOMAC Pain Score, including changes from baseline will be summarized by study visit and dose level / treatment.

The number of subjects achieving at least a 30% improvement from baseline in WOMAC Pain Score will be summarized by study visit and dose level / treatment.

Reported values and calculated changes from baseline in WOMAC Function Score, in total and individual BPI, and in KOOS will be summarized by study visit and overall.

For the patient response, the number of subjects in each of the response categories will be summarized by study visit and dose level / treatment. The change from baseline in patient response will be summarized by study visit and dose level / treatment.

#### 9.3. Efficacy Analysis

All inferential analyses of efficacy will be based on the first 180 days after dose administration (Stage A) and on the analysis of time from Day 0 until patient request for a second injection.

CONFIDENTIAL Page 18 of 27

Final 2.0, 11 Oct 2021

Sponsor: Xalud Therapeutics, Inc.

Protocol No.: XT-150-2-0204

[figure not shown]
For the statistical analysis of the primary efficacy endpoint, a logistic regression (response: 30% improvement at Day 180 (yes/no)) will be performed to compare 150 µg XT-150 with placebo and 450 µg XT-150 with placebo statistically. The model will include a fixed effect for treatment and the subject's baseline WOMAC pain score as a covariate. From this model, the 150 µg XT-150 to placebo and 450 µg XT-150 to placebo odds ratio of reduction and its two-sided 95% CI will be calculated. In this analysis, a subject who does not provide a response at Day 180 will be considered a non-responder (i.e., improvement will be set to "no").

In the event that one or more treatment arms has no responders, which would cause numerical difficulties in the logistic regression model, the statistical analysis will add 2 successes and 2 failures to each treatment group. This based on the recommendation in Agresti and Caffo, "Simple and Effective Confidence Intervals for Proportions and Differences of Proportions Result from Adding Two Successes and Two Failures," The American Statistician, Vol. 54, No. 4 (Nov., 2000), pp. 280-288.

The change from baseline in WOMAC Function Score will be analyzed using a repeated measures model including fixed effects for treatment (i.e., 150 µg XT-150, 450 µg XT-150, placebo), study day (i.e., Day 7, 30, 60, 90, 120, 150, 180) and treatment by study day interaction. In addition, the subject's baseline score will be included as a covariate. From the model, the treatment differences between 150 µg XT-150 and placebo, and 450 μg XT-150 and placebo will be estimated for the average effect of the first 180 days after dose administration (i.e., Stage A). Additionally, p-values and corresponding two-sided 95% confidence intervals will be provided.

The change from baseline in WOMAC Pain Score will be analyzed similarly.

Change from baseline in total and individual BPI, change from baseline in KOOS, and change from baseline in the patient response will be analyzed similarly.

CONFIDENTIAL Page 19 of 27

Final 2.0, 11 Oct 2021

Protocol No.: XT-150-2-0204 Sponsor: Xalud Therapeutics, Inc.

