4.0 BACKGROUND AND RATIONALE

4.1 XT-150

Complete and current information on XT-150 can be found in the Investigator's Brochure (IB) version 7, 24 May 2019.

XT-150 is a new treatment for chronic pain from pathogenic inflammation. It is a plasmid designed to transiently express a variant of the anti-inflammatory cytokine, interleukin-10 (IL-10).

The mechanism of action of XT-150 is through a reduction in inflammation. XT-150 returns target tissues to normal function by induction and release of a single-amino acid variant human IL-10 (a human anti-inflammatory cytokine, IL-10var), that acts to modulate inflammation through multiple pathways: Suppressing pro-inflammatory cytokine production and release, down-regulating cytokine receptors and up-regulating antagonists; and inhibiting hydrogen peroxide and nitric oxide production (Moore 2001; Sawada 2001).

When XT-150 is administered by injection at the site of chronic inflammation, low levels of human IL-10var protein are produced over the following weeks, which reduces the pain associated with joint inflammation.

Additionally, the targeted delivery of XT-150 directly to the joint knee space restricts the potential for systemic AEs.

XT-150 presents a treatment opportunity for patients suffering significant damage from osteoarthritis, such as those in need of knee replacement; or the many patients who are not good surgical candidates for knee replacement. This study will help select doses to establish safety, tolerability, and effectiveness in subsequent clinical trials.

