13.5.1 Multiplicity of endpoints

The statistical analysis of the primary endpoint will preserve a familywise error rate of 0.025 (one-sided), accounting for statistical tests of each of the two XT-150 doses to placebo with respect to the primary endpoint.

[figure not shown]
P-values from analyses of other endpoints may be interpreted as descriptive statistics.

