#### 9.4. Adjustment for Multiplicity

Two endpoints will be subject to multiplicity adjustment: The primary endpoint (achievement of a 30% reduction in WOMAC pain)

This will be accomplished by first testing for significance of the two active doses of XT-150 versus placebo with respect to the primary endpoint at the 0.025 level, one-sided. This addresses the multiplicity of doses with respect to the primary endpoint. Then a Dunnett test for the 50% endpoint will be performed at the alpha remaining after having done the first Dunnett test. Using only the remaining alpha for this additional endpoint continues to control the overall false positive rate at 0.025, one-sided. The numerical value of this remaining alpha depends on the primary (30% endpoint) Dunnett test as follows:

[figure not shown]
- If both doses are significantly better than placebo, then the remaining alpha is the full 0.025 level.
- If exactly one of the two active doses is significantly better than placebo, then the alpha remaining will be determined by the software performing the primary Dunnett test. (If the statistical analysis was of Gaussian group means, with N=90 per group, the remaining alpha would be 0.0115 (one-sided); the actual alpha may be different, because the model includes a covariate and the sample sizes may not be exactly 90 per group.)
- If neither active dose is significantly better than placebo, then no alpha remains and no inferential testing will be performed.

Achievement of a 30% improvement in WOMAC Pain score at Day 180 will be analyzed using a logistic regression model as described in Section 9.3 to preserve a familywise error rate of 0.05 (two-sided),

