#### 10. CHANGES FROM THE ANALYSIS PLANNED IN THE PROTOCOL

Although the protocol called for step-down statistical testing using the Dunnett approach, the Dunnett testing will not use step-down testing, because it would exhaust the 'alpha' available for additional statistical testing. By not using the step-down approach, it is permissible to continue statistical testing provided that at least one of the treatment arms is statistically significantly different from the control group, with respect to the primary endpoint.

CONFIDENTIAL Page 20 of 27

Protocol No.: XT-150-2-0204 Sponsor: Xalud Therapeutics, Inc.

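### Does leaving the 95% CIs for the two primary odds ratios unadjusted, beside a Dunnett-adjusted test, put the primary conclusion at risk?

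*SAP*

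**What the plan says.** SAP section 9.3 analyses Day 180 response by logistic regression: "The model will include a fixed effect for treatment and the subject's baseline WOMAC pain score as a covariate". From that model, each dose's "odds ratio of reduction and its two-sided 95% CI will be calculated". No adjustment is named. The same section asks for two-sided 95% confidence intervals for the continuous endpoints, also without qualification.

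The decision rule stands elsewhere. Protocol section 13.5.1: "The statistical analysis of the primary endpoint will preserve a familywise error rate of 0.025 (one-sided"). SAP section 9.4 tests the "two active doses of XT-150 versus placebo with respect to the primary endpoint at the 0.025 level, one-sided". SAP section 10 makes this single-step: "the Dunnett testing will not use step-down testing". Section 9.4 then sets out what follows if both doses, exactly one, or neither is significant. For the middle case, with Gaussian means and 90 per group, "the remaining alpha would be 0.0115 (one-sided").

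The last sentence of section 9.4 says that the 30% response "will be analyzed using a logistic regression model as described in Section 9.3 to preserve a familywise error rate of 0.05 (two-sided"). In the public text it stops at a comma.

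**The concern.** The test and the interval appear to use different yardsticks. Dunnett demands more of each dose than an ordinary 95% CI does, because it allows for two comparisons. A dose could be reported as not significant beside an odds ratio whose interval lies wholly above 1. The odds ratio with its CI is the only primary effect estimate that section 9.3 names, and protocol section 4.1 says: "This study will help select doses to establish safety, tolerability, and effectiveness in subsequent clinical trials". If readers took the two intervals as tests, the chance of at least one false positive would exceed the planned 2.5% one-sided. If that were how the trial reached its conclusion, it would be a real defect.

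**Working it through.** **Inputs.** 90 per Stage A arm and response rates of 10% and 30% (SAP section 4.5); 0.025 one-sided over two doses and a remaining alpha of 0.0115 (section 9.4); single-step Dunnett (section 10).

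**1. The plan's own figure.** For two comparisons that share a control of equal size, the correlation is 0.5. Solve 1 − Φ₂(c, c; 0.5) = 0.025. This gives c = 2.212, a per-dose one-sided p of 0.01348, and a remainder of 0.025 − 0.01348 = 0.01152. With t on 267 df, c = 2.224 and the remainder is 0.01151. Both round to the stated 0.0115.

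**2. The gap.** An ordinary 95% CI excludes 1 on the benefit side when z > 1.960. The test passes when z > c. For z between 1.960 and c the two differ. Because c exceeds 1.960 for any correlation below 1, the gap always exists if the intervals are ordinary.

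**3. The cut-off at the planning rates.** The value 2.212 assumes correlation 0.5. On the log-odds scale the placebo arm has the larger variance:
- placebo: 1/(90 × 0.1 × 0.9) = 0.1235
- each active arm: 1/(90 × 0.3 × 0.7) = 0.0529
- correlation: 0.1235/(0.1235 + 0.0529) = 0.70

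At correlation 0.70, c = 2.180. Section 9.4 anticipates this kind of shift, since it leaves the actual value to the software.

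**4. How often they differ.** Simulation with Wald log-odds z and no covariate (the documents give no value for its effect). The fixed cut-off used 2,000,000 trials at 10% vs 30% and 400,000 in the other rows. For 10% vs 30% and the null, the last column used 1,000,000 trials with each trial's own correlation.

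| Placebo vs active | At least one dose differs, cut-off 2.212 | Same, cut-off matched to the correlation |
|---|---|---|
| 10% vs 30% | 9.2% | 8.0% |
| 10% vs 25% | 18.4% | 16.6% |
| 15% vs 30% | 20.4% | 17.7% |
| 10% in all arms | 2.1% | 1.9% |

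At 10% vs 30% with the matched cut-off, the rate is 4.2% per dose, and in 1.7% of trials no dose passes while an interval excludes 1. With the fixed cut-off, 7.1 of the 9.2 points are trials in which the other dose passes.

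**5. An example.** Placebo 9/90, active 19/90:
- OR = (19 × 81)/(9 × 71) = 2.41; log OR = 0.879
- SE = √(1/19 + 1/71 + 1/9 + 1/81) = 0.436
- z = 0.879/0.436 = 2.016; one-sided p = 0.0219
- ordinary CI: 1.02 to 5.66
- lower limit with multiplier 2.212: 0.92; with 2.180: 0.93

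The test fails while the ordinary interval excludes 1. With 20/90, z = 2.180 and the result is on the boundary. With 21/90, z = 2.339 and the two agree.

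**6. Error rate.** In large samples under the global null at correlation 0.5, the chance that at least one ordinary interval lies wholly above 1 is 1 − Φ₂(1.960, 1.960; 0.5) = 4.5%. For the test it is 2.5%. The planned claim rests on the test, so the rate that applies is 2.5%.

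**7. Does any rule use the interval?** Section 9.4's three branches (both, one or neither dose significant) refer only to the test. Nothing legible in sections 9.3, 9.4 or 10 draws a conclusion from a CI. Protocol section 4.1 is a general statement of purpose and sets no dose-selection rule.

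**The case for a change.** The best argument for a change is that section 9.3 is a complete sentence, names no adjustment, and concerns the estimate that readers will look at first. Single-step Dunnett has matching simultaneous intervals, so one sentence and an output option would align interval and test. At the weaker effects in the plan's power table the two would differ in 17% to 18% of trials even with the matched cut-off. A reader comparing doses could be puzzled.

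The factual part stands: ordinary intervals can differ from the test, and the legible text does not say which type is meant. The inference to a fault does not. Reporting per-comparison intervals beside an adjusted test is a common and defensible choice, because each interval then answers its own question at its stated coverage. Simultaneous intervals have a cost too: they are about 11% wider on the log-odds scale at the planning rates (2.180/1.960 = 1.112) and 13% at correlation 0.5. A multiplier fixed in advance at 2.21 would bring in a small mismatch of the opposite kind, since a dose with z between about 2.18 and 2.21 could pass the software's test while its interval included 1.

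Nor can the silence be held firmly against the plan. The closing sentence of section 9.4 ties the section 9.3 model to a two-sided familywise rate of 0.05, the natural counterpart of simultaneous two-sided 95% intervals, and is then cut off. Whether the missing words define the intervals cannot be settled from the public text.

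**Conclusion.** The concern does not hold. Followed as written, sections 9.3 and 9.4 give a valid estimate with a valid per-comparison interval and a test that controls the familywise error at 2.5% one-sided. Interval and test can differ, in about 8% of trials at the planning rates and about 1.9% with 10% in every arm, but no conclusion in the plan depends on the interval. In the planning case both doses truly work, so an interval above 1 does not mislead about direction. What is left is a missing label and a preference for matched intervals.

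This rests on three assumptions: the intervals are ordinary (if the cut-off text makes them simultaneous, the question disappears); no redacted text gives the CI a decision role; and the covariate changes the frequencies only modestly. On the last point, with the cut-off at 2.212, a simulated covariate effect between −0.7 and 0.3 log-odds per SD gave 7.1% to 8.9% at the planning rates.

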8.7.1 Prohibited medications

The following treatments are prohibited prior to study drug administration:

- Current treatment with antibiotics or antiviral agents, except as topical treatments.
- Current treatment with immunosuppressive agents
- Current treatment with anti-platelets or anticoagulants. Aspirin ≤325 mg/day is allowed
- Current use of systemic corticosteroids
- Alcohol or illicit drug abuse within 1 year before the screening visit

Concomitant medications for pain will be allowed at doses and frequencies prescribed prior to the study treatment. New medications or escalation of pre-study treatments will be captured on CRFs during the 360-day evaluation period.

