8.7.2 Rescue Medications

Acetaminophen ($\leq 3,000 \text{ mg}$ in 24 hours) will be allowed as rescue medication.

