13.1 Determination of Sample Size

A total of 270 subjects will be randomized to the 3 treatment groups in a 1:1:1 ratio. The sample size of 90 subjects per group provides more than 90% power to detect a greater responder rate in at least one XT-150 group compared to placebo and 85% power to detect both arms superior to placebo, assuming the responder rate is 30% in each XT-150 group and 10% in the placebo group. As a sensitivity analysis of different assumptions on the response rates in the placebo and XT-150 groups, Table 7 shows the statistical power to detect that at least one treatment group provides greater response than placebo and to detect that both treatment groups provide greater responses.

		Statistical Power (%)				
Placebo response rate (%)	XT-150 response rate (%) in both treatment arms	To detect at least one treatment arm superior to placebo	To detect both treatment arms superior to placebo			
10	25	78	57			
	30	95	85			
	35	99	97			
15	25	38	18			
	30	70	46			
	35	91	77			

Table 7. Treatment Effect That Can Be Detected

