13.5.2 Statistical methods for the binary outcomes

Whether the subject achieves at least a 30% improvement from baseline in WOMAC Pain Score at Day 180 will be coded as a binary outcome: responder or non-responder. Subjects who withdraw from study before Day 180 or otherwise do not provide a response at that time point will be considered non-responders. The response outcome will be analyzed in a logistic regression model with treatment as the main factor and baseline WOMAC pain as a covariate. Within this model, z-tests will be used to compare the two XT-150 doses to placebo, with step-down Dunnett-like adjustments for multiplicity of doses. Handling of special cases, such as zero responders in a treatment group, will be addressed in the SAP.

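### The Day 180 responder rule has no provision for index-knee surgery, non-study Index Knee injections or changed analgesics, so relief from these can count as response to the study injection

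*SAP*

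**What the plan says.** SAP 5.5 and 9.3 define response by the Day 180 WOMAC Pain score relative to baseline. Two statements override that score:

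- SAP 9.3: "In this analysis, a subject who does not provide a response at Day 180 will be considered a non-responder".
- Protocol 13.5.2: "Subjects who withdraw from study before Day 180 or otherwise do not provide a response at that time point will be considered non-responders". SAP section 10, which lists departures from the protocol, does not withdraw the protocol's reference to withdrawal.

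Other pain treatment is handled elsewhere, without any link to the responder definition:

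- Protocol 8.7.1 introduces its list with "The following treatments are prohibited prior to study drug administration", so the list governs the period before dosing.
- The limits on hyaluronic acid, stem-cell and glucocorticoid knee injections are entry criteria (Protocol 7.2, criteria 7 and 8).
- Protocol 8.7.1 permits pain medication at its pre-study dose and frequency, then adds: "New medications or escalation of pre-study treatments will be captured on CRFs during the 360-day evaluation period". Protocol 9.5 and 9.6 have changes in drug regimen or pain therapy recorded at each visit.
- Under Protocol 8.7.2, acetaminophen up to a daily limit "will be allowed as rescue medication".
- Exclusion criterion 3 has participants agree not to schedule a knee replacement in Stage A. No section says how one is analysed if it happens.

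SAP section 3 lists ICH E9(R1) as relevant guidance. The readable text names no estimand, no strategy for these events and no sensitivity analysis of the primary endpoint.

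**The concern.** Protocol 5.0 asks about the analgesic efficacy of a single intra-articular dose. A 30% fall in pain after an operation on that knee, or after someone else's injection into it, says little about that dose, yet the rule scores it as success. The same holds less sharply for a new or stronger analgesic.

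The comparison is affected because the arms differ in how many participants can be converted. Under the plan's assumed rates, 90% of placebo participants and 70% of XT-150 participants are non-responders. Even equal use of other treatment therefore adds more responders on placebo. If participants with uncontrolled pain seek help more often, the placebo excess grows. Protocol 4.4.1 points this way, since it lists a lower need for pain medication and therapies among the potential benefits of XT-150. If use were instead higher on XT-150, other treatment could be credited to the drug.

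**Working it through.** **Inputs from the documents.** Protocol 13.1: "270 subjects will be randomized to the 3 treatment groups in a 1:1:1 ratio", with 90 per group and responder rates of 10% (placebo) and 30% (each XT-150 dose). Protocol 13.5.1: familywise error 0.025, one-sided, over the two dose-placebo tests. Protocol 13.5.2 uses step-down Dunnett; SAP section 10 replaces it with single-step Dunnett.

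**The plan's own figure.** Table 7 gives 95% for at least one dose and 85% for both at 10% vs 30%. With two comparisons sharing a control (correlation 0.5), the Dunnett cut-off c solves P(Z1 ≤ c, Z2 ≤ c) = 0.975, so c = 2.212, or 0.01348 per comparison. Simulated Fisher tests with step-down (second test at 0.025) give 94.9/83.5. The stated pair reproduces within 2 points.

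**Illustration.** Assumptions, none from the documents: the plan's 10% and 30% exclude relief from other treatment; a share u of those who would not otherwise respond use other treatment; it succeeds in a fraction s = 0.5. Then

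observed rate = p + (1 − p) × u × s.

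For example, placebo with u = 10%: 0.10 + 0.90 × 0.10 × 0.5 = 14.5%. XT-150 with u = 5%: 0.30 + 0.70 × 0.05 × 0.5 = 31.75%.

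Power is simulated for three binomial arms of 90, using the log-odds Wald z without the baseline covariate, and single-step Dunnett at 2.212 as in the SAP:

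| Use, placebo / XT-150 | Observed rates | Difference (points) | Odds ratio | Power, at least one / both (%) |
|---|---|---|---|---|
| none | 10.0% vs 30.0% | 20.0 | 3.86 | 96/80 |
| 10% / 10% | 14.5% vs 33.5% | 19.0 | 2.97 | 90/66 |
| 10% / 5% | 14.5% vs 31.75% | 17.25 | 2.74 | 84/55 |
| 5% / 10% | 12.25% vs 33.5% | 21.25 | 3.61 | 96/81 |

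The base row differs from 95/85 because the test and the Dunnett form differ, not because of other treatment.

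**The opposite direction.** Suppose the drug has no effect, and 10% of placebo and 20% of XT-150 non-responders are converted (use times success). The rates become 0.10 + 0.90 × 0.10 = 19% and 0.10 + 0.90 × 0.20 = 28%, and at least one dose is declared superior in about 31% of simulated trials. With 10% converted in every arm, the figure is about 2%.

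**How much a rule on surgery and injections recovers.** Assume a fifth of the use in the 10% / 5% row is surgery or injection. Setting those users to non-responder leaves 8% and 4%:

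- placebo: 0.10 + 0.90 × 0.08 × 0.5 = 13.6%
- XT-150: 0.30 + 0.70 × 0.04 × 0.5 = 31.4%

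Power is then about 88/61, against 84/55 without the rule. Most of the loss in that row comes from analgesics. This leaves out anyone who would have responded anyway and also had surgery or an injection.

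**The case against.** **Treatment policy is legitimate.** Scoring Day 180 pain whatever else was taken is a recognised strategy. This stands, but the plan neither states nor justifies it, and it fits poorly with a question about one injection when the other event is surgery on the same knee.

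**The plan is not silent on these treatments.** Pain medication is allowed at its pre-study level, so escalation is arguably a deviation, and Protocol 13.9 summarises deviations by group. Non-compliance and perceived lack of benefit are withdrawal reasons (Protocol 7.4.1), and withdrawal before Day 180 means non-response. Some of these participants may therefore already be non-responders. Those who stay in the study and give a score are not.

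**Power loss against plan.** A reader might infer that the trial loses power relative to its stated 95/85. The documents do not support that. The 10% and 30% in Protocol 13.1 and SAP 4.5 are rates for the endpoint as defined; nothing says that they exclude relief from other treatment.

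**Certain dilution.** A reader might also infer that the rule necessarily dilutes the effect. It does not: the 5% / 10% row shows no loss of power. Protocol 4.4.1 lists a potential benefit, not an observed pattern of use.

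**Redaction.** Protocol 8.7.3 and 9.4 and SAP 11.1 cannot be read, so a rule placed there cannot be excluded. The primary-analysis paragraphs in Protocol 13.5.2 and SAP 9.3 do read as complete.

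**Conclusion.** The gap holds in the readable text: only withdrawal before Day 180 or a missing Day 180 score overrides the observed result. Index-knee surgery, a non-study Index Knee injection and a changed analgesic regimen can each produce a responder.

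The direction of bias depends on use by arm. It is towards no difference if use is equal or higher on placebo, and can favour XT-150 if use is higher there. The placebo-heavy pattern is the more plausible one, but it is not established.

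The size is unknown. The power figures rest on assumed usage, an assumed 50% success rate and the assumption that the plan's rates exclude other treatment. They show sensitivity only. This is a worthwhile improvement to the primary analysis, not proof that the trial is underpowered.

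**What to change.** In SAP 9.3, before unblinding:

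1. Count a subject with index-knee surgery or a non-study intra-articular injection into the Index Knee before the Day 180 score as a non-responder, whatever the score. Keep the protocol's withdrawal rule, and apply the same definition to the 50% endpoint in SAP 9.4. This follows the logic already used for missing scores.
2. Pre-specify a sensitivity analysis that also counts subjects with a new or escalated analgesic regimen before Day 180 as non-responders, classified blind from the CRF. Report the score-as-observed (treatment-policy) result alongside.

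The SAP addendum says that it was written after database lock and unblinding. A rule added after that point has to be labelled post hoc.

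The cost is SAP wording and a blinded review of data already collected. Observed responder rates fall slightly, and the change in item 1 recovers only the part of any distortion that is due to surgery or injection. These are analysis rules only and alter no treatment or rescue provision.
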